#### STUDY PROTOCOL:

# The Holographic Standardized Patient: Using Mixed Reality to Reduce Barriers to Crisis Simulation in Acute Care

#### **Background and Rationale:**

The current state-of-the-art in medical simulation and assessment is mannequin based and reliant on highly specialized personnel, equipment, and dedicated space. Costs are exorbitant and therefore access is limited. Health care facilities and educational institutions without such a model are unable to participate in high fidelity medical simulation for initial training, continuing medical education, and assessment purposes. Simulation centres are also limited to trainees able to easily reach their facilities, which means lost potential revenue and impact. In addition, in-person evaluation is also vulnerable to disruption from the current pandemic, and alternatives are needed which allow evaluation.

We have created a prototype platform, HoloSIM, which disrupts this model. HoloSIM is a mixed reality platform consisting of laptop- or tablet-based instructor software and Microsoft Hololens 2 headset-based student software. The Microsoft Hololens 2 allows for mixed reality: spatially stable, interactable, and animated holograms inserted into a user's workspace (See Figure 1).

**Figure 1:** HoloSIM allows instructors to view a composite video of students interacting with the mixed reality learning environment. Follow this link to see a video of a prototype HoloSIM mixed reality learning environment (as experienced by a student).

This permits the augmentation of existing operating rooms and training spaces with holographic (i.e. virtual) equipment and patients. In addition, ubiquitous resources such as cardiopulmonary resuscitation (CPR) training mannequins may be extended to have animations, interactivity, and dynamic visual features as required.

**Figure 2:** This image depicts the student's mixed reality view of a holographic patient with the symptoms of anaphylaxis (red facial rash and new wheeze). Breath sounds are auscultated by moving a holographic stethoscope over the correct area of the virtual patient. Follow this link to see a simulated patient experiencing anaphylaxis.

Telesimulation capable platforms are defined as being capable of controlling medical simulations for education, training, and assessment at off-site locations. A wide variety of medical emergencies can be initiated using the HoloSIM instructor software, and then monitored/controlled from any distance using a high-speed internet connection. There are no reports, to our knowledge, of a mixed reality telesimulation-capable platform such as HoloSIM. However, the platforms usability, desired frequency and subject matter of use, and the barriers to adoption require investigation.

Though infrequent, anaphylaxis is a high risk and complex crisis seen in all acute care specialties; this scenario requires a focused examination and rapid decisive action, which presents a challenge for trainees. Failure to effectively identify and treat anaphylaxis can lead to severe patient harms. We have therefore selected it as an archetypal medical crisis model to test the effectiveness of HoloSIM in learner acquisition of technical and nontechnical skills, scenario related declarative knowledge, as well as learner perceptions of this novel assessment method.

Mixed reality technology could potentially create infinite numbers of immersive clinical scenarios. By validating its effectiveness as an educational and assessment tool with this study we aim to demonstrate its feasibility in enhancing medical education curricula. This modality could provide a lower cost learning and assessment platform that can align with any context-specific clinical practice and professional development. With the telesimulation abilities allowing it to be applied locally and internationally, this solution may advance clinical teaching and assessment in a wide-ranging manner. Therefore, the use of a mixed reality high fidelity simulation model may allow for significant cost savings and increased access to simulation training and evaluation both within, and outside of, academic centres.

### **Hypothesis/Research Questions:**

In this study we propose to refine and evaluate an innovative holographic medical crisis simulation technique which can be used both as an assessment tool and for teaching technical and nontechnical skills in a novel simulation curriculum.

Two main research questions will be addressed:

- 1. Does the novel simulation platform have sufficient usability for regular teaching and assessment use?
- 2. Is a mixed reality simulation platform curriculum non-inferior to the current teaching and assessment standard of high-fidelity mannequin-based crisis simulation in terms of student acquisition of technical and non-technical skills?

This study is the first known research initiative aiming to demonstrate that a mixed reality simulation training and assessment solution is usable and can improve decision making skills and management in a complex crisis scenario. We hypothesize the HoloSIM platform is non-inferior to traditional mannequin-based simulation in acquiring and assessing technical and non-technical skills in a model life threatening health condition (e.g. anaphylaxis).

## **Research Design and Methodology**

### Platform design:

We have created the prototype HoloSIM mixed reality simulation platform utilizing an iterative development process through resident morning teaching rounds over the past year. Immersed in the mixed reality simulations, learners undertake the decision-making steps in managing the medical care for a patient with an acute medical crisis. They then navigate through the scenarios that—by instructor control—provide feedback depending on their actions in the form of either the patient's hemodynamic changes, verbal prompts from the holographic patient in the scenario, or a holographic medical team confederate. We have designed the HoloSIM 'student experience' for use with typical Hololens controls of intuitive hand gestures and directing visual gaze towards holographic areas of interest. A limited set of dialogue, facial expressions, animations, clothing, skin visual cues, auscultations, physical exam findings, holographic confederates, and patient monitor physiologic changes have been incorporated to date. However, the underlying prototype program structure has been designed to allow this catalogue to be rapidly and easily expanded, allowing the software to be used to simulate a practically limitless variety of crisis scenarios.

#### Overall Experimental Strategy and Workflow:

The success of this proposal rests on our ability to optimize and adapt the HoloSIM platform to educate and assess acute care medical residents; the two research questions will be addressed by separate study phases. In the first phase of the study, the focus will be on software/scenario development and usability testing of the student and instructor experience. In the second study phase the HoloSIM platform will be incorporated into a

novel anaphylaxis education and assessment curriculum for acute care residents with the impact on technical and nontechnical skills, scenario related declarative knowledge, as well as learner perceptions of the novel assessment tool evaluated by randomized control trial.

First Research Question (Study Phase I): Software/Scenario Development and its Usability Evaluation

To address *the first research question*, throughout the first study phase we will follow best practices in software development for optimizing medical education software usability to maximize the impact of the final software. By doing so the project development team will:

- Ensure participation from all target user groups as both instructors and students.
- Test usability iteratively and systematically with the product under development, not solely with the final product. Testing will occur *in situ* when possible, within unused clinical areas which participants typically use as clinical and teaching workspaces.
- Use a broad representation of participants in terms of technological as well as simulation teaching experience.

Upon receiving institutional research ethics approval, an initial two-month piloting period will allow the creation of two mixed reality anaphylaxis scenarios. The first scenario will be drawn from a recent trial of a telesimulation compatible mannequin based simulation system^8, which is similar to other anaphylaxis scenarios used in Critical Care, Anesthesia, and Emergency Medicine literature, , . The second scenario  involves different inciting events, patient characteristics, hemodynamics, and environmental stimuli. However, the same core anaphylaxis management concepts are required. These scenarios will then be piloted on medical students, residents, staff anesthesiologists, and other experts in the field not involved in the study.

## Recruitment and Study Groups:

Participants from acute care postgraduate training programs at Sunnybrook Health Sciences Centre, a tertiary academic institution, will be recruited for 1-hour sessions via email invitation. Consent will be obtained via REDCap at the time of recruitment, as well as a questionnaire to survey demographic information and previous experience with simulation and immersive reality technologies. This will include resident learners of all levels, recruited to use the software in the student role while paired with staff physicians (i.e. instructors/assessors) from the same specialty using the software in the instructor role, drawn together from the same fields of Anesthesiology (Group 1), Internal Medicine (Group 2), Critical Care Medicine (Group 3), or Emergency Medicine (Group 4).

Instructors will be informed two weeks in advance that the session content will include time for orientation to mixed reality, free experimentation, an anaphylaxis scenario, as well as a scenario of their choosing drawn from a study generated database of publicly available peer reviewed content within their specialty, , .

Usability evaluation:

The pairings will use HoloSIM to conduct medical crisis simulations in both a structured and unstructured manner. Usability will be assessed in an ethnographic manner using audio recorded semi-structured interviews with thematic analysis. Usability will also be assessed via the System Usability Scale(SUS), a widely cited, validated, and industry standard Likert scale questionnaire (see Supplementary Figure 4) utilized across a variety of software platforms. No validated tools exist to specifically assess mixed reality software, however a comprehensive multidomain Likert questionnaire, will be administered (previously developed to assess a mixed reality medical simulation learning tool) to students to delineate factors that enhance or limit learning via the Hololens 2 headset and HoloSIM. Additional Likert items will assess the participants age, previous experience with simulation-based teaching, and their desired frequency of future use of the platform.

An iterative process will be undertaken to improve the user experience of participants in both the student and instructor roles through the aid of rapid prototyping, each session prompting refinement and feature addition both pre and post. Significant feature and crisis scenario addition based on user feedback is expected as well as efforts related to discovery and remedy of software errors/failures. We expect the final product educational and assessment software will provide a unique opportunity for knowledge and skills acquisition as well as assessment in a variety of clinically relevant training scenarios. As the medium of mixed reality is in its infancy, we will also learn potential accessibility issues and barriers to use.

The study team and all academic collaborators are committed to the principles of Free and Open Access Medical education (FOAM) with regards to HoloSIM. All software code and resources developed related to this grant will be made freely available via our website and the software repository github. This will enable other groups to modify or adapt our work as per their needs.

#### Study conduct and data collection/management:

A total of 6 sessions within each specialty will be planned (24 sessions with 48 total participants), or until interim analysis demonstrates thematic saturation. This is in keeping with data demonstrating 5-6 of any type of user is typically enough to reveal 95% of usability issues.

## Statistical Analysis:

SUS and mixed reality specific questionnaire results will be compiled in aggregate and descriptive statistics will be presented as frequencies. For the items of the SUS, the score will be calculated using Brooke's standard scoring method.

Second Research Question (Study Phase II): Evaluation of the novel mixed reality based anaphylaxis curriculum as a teaching and assessment tool

In the second study phase the HoloSIM platform will be incorporated into a novel anaphylaxis education and assessment curriculum and evaluated by randomized control trial. The primary outcome will be the impact on technical and nontechnical skill

acquisition as assessed by performance checklist; secondary outcomes include the scenario related declarative knowledge assessed by multiple choice quiz, as well as learner perceptions of the mixed reality assessment tool as measured by questionnaire. The nature, timing, and validity of these measurement tools is outlined below.

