## Study follow-up:

We will invite participants to return one month later to assess the impact of the intervention with a validated anaphylaxis knowledge test developed by allergists for use with the same curriculum included in our study and a mannequin-based anaphylaxis assessment scenario, the parameters of which were piloted in the first study stage utilizing HoloSIM. Participants from the intervention group (Group A) will be oriented to the mannequin simulation environment prior to managing the scenario as they will not have had previous exposure to this modality. All participant sessions will be video recorded and evaluated by two trained assessors. Scoring of the assessment scenario will involve a weighted checklist (See Supplementary Figure 6) of critical events similar to other validated anaphylaxis scoring tools and used in a previous similar trial. Scores in percentage points will be averaged between assessors, with a significant deviation being referred to a third assessor.

[figure not shown]

Figure 3: Study Design

Study limitations:

We understand that participants in Group B (Control) will be learning on and then assessed using the same modality (mannequin-based simulation), which creates an advantage for these participants. However, practice and assessments cannot be done on live patients, and the current gold standard is mannequin-based simulation training. Thus, there are no alternatives but to compare HoloSIM to mannequin-based simulation.

We acknowledge that no pretesting will be performed prior to the intervention, this is to avoid repeated exposure to anaphylaxis related content immediately prior to the intervention. However, we have randomized carefully to avoid bias.

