## Figure 5: Simulation Effectiveness Tool (SET-M)

#### Simulation Effectiveness Tool - Modified (SET-M)

After completing a simulated clinical experience, please respond to the following statements by circling your response.

PREBRIEFING:	Strongly Agree	Somewhat Agree	Do Not Agree
Prebriefing increased my confidence	3	2	1
Prebriefing was beneficial to my learning.	3	2	1
SCENARIO:			•
I am better prepared to respond to changes in my patient's condition.	3	2	1
I developed a better understanding of the pathophysiology.	3	2	1
I am more confident of my nursing assessment skills.	3	2	1
I felt empowered to make clinical decisions.	3	2	1
I developed a better understanding of medications. (Leave blank if no medications in scenario)	3	2	1
I had the opportunity to practice my clinical decision making skills.	3	2	1
I am more confident in my ability to prioritize care and interventions	3	2	1
I am more confident in communicating with my patient.	3	2	1
I am more confident in my ability to teach patients about their illness and interventions.	3	2	1
I am more confident in my ability to report information to health care team.	3	2	1
I am more confident in providing interventions that foster patient safety.	3	2	1
I am more confident in using evidence-based practice to provide nursing care.	3	2	1
DEBRIEFING:			
Debriefing contributed to my learning.	3	2	1
Debriefing allowed me to verbalize my feelings before focusing on the scenario	3	2	1
Debriefing was valuable in helping me improve my clinical judgment.	3	2	1
Debriefing provided opportunities to self-reflect on my performance during simulation.	3	2	1
Debriefing was a constructive evaluation of the simulation.	3	2	1
What else would you like to say about today's simulated clinical experience?			

Figure 6: Anaphylaxis Checklist of Core Decision Making Steps

History (10 points)  Symptom duration [1]  Inciting factors [2]  Airway management questions (i.e. sob) [2]  Other symptoms [1]  Past medical history [1]  Medications [1]  Allergies [2]  Physical (15 points)  Airway assessment [3]  Breath sounds [3]  Pulse oximetry [3]  Respiratory rate [2]  Cardiac exam [1]  Blood pressure [1]  Pulse [1]  Extremity/skin [1]

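### The non-inferiority claim covers technical and non-technical skills, but the only observed performance measure is one checklist total of clinical steps with no non-technical component

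*Protocol*

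**What the plan says.** Under Hypothesis/Research Questions, the protocol asks whether the mixed reality curriculum is non-inferior to mannequin-based simulation "in terms of student acquisition of technical and non-technical skills". The hypothesis in the same section names both kinds of skill again.

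The introduction to the Second Research Question (Study Phase II) sets the primary outcome: "The primary outcome will be the impact on technical and nontechnical skill" and, continuing the sentence, "acquisition as assessed by performance checklist". One instrument therefore stands for both constructs.

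Study follow-up gives the instrument: "Scoring of the assessment scenario will involve a weighted checklist", which is Figure 6, titled "Anaphylaxis Checklist of Core Decision Making Steps". Its scored blocks are history, physical and management. Two trained assessors score from video, and their scores are averaged.

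Sample Size Calculation and Feasibility sets one limit, 3 points out of 45. The Phase II Statistical analysis section compares mean checklist scores between the groups. Non-technical skill is not defined anywhere in the protocol.

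**The concern.** The stated construct is wider than what the instrument records. If the plan is followed exactly, a checklist difference within 3 points answers research question 2 as worded, and that wording includes non-technical skills. Yet the score has no part that could be pointed to as the non-technical result.

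This matters more in a non-inferiority trial than in a superiority trial. A construct that the score does not separately capture cannot produce a separate unfavourable difference, so the claim about it passes along with the total. A later analysis plan could not repair this, because the protocol collects no rating from which a non-technical result could be computed.

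**Working it through.** **Step 1. Reproduce the 45-point scale.** The inputs are the item weights in Figure 6.

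| Block | Weights | Items | Points |
|---|---|---|---|
| History | 1+2+2+1+1+1+2 | 7 | 10 |
| Physical | 3+3+3+2+1+1+1+1 | 8 | 15 |
| Diagnostic evaluation | none | 0 | 0 |
| Management | 3+3+2+1+2+3+1+1+1+1+1+1 | 12 | 20 |
| Total | | 27 | 45 |

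The block totals agree with the figure's own labels (for example "History (10 points" and "Physical (15 points", each followed by a closing bracket), and the sum agrees with the 45 points in the sample size section.

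**Step 2. Sort the items by what they credit.**
- The 15 history and physical items (10 + 15 = 25 points, 25/45 = 55.6%) credit a question asked, or an examination or measurement made.
- The 12 management items (20 points, 20/45 = 44.4%) credit treatment, monitoring or disposition.
- Items that rate leadership, task allocation or teamwork: 0 of 27.
- The nearest item to communication between clinicians is Notify PMD, at 1 point: 1/45 = 2.2%.

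**Step 3. Compare with the limit.** The limit is 3/45 = 6.7% of the scale. If every control participant earned the Notify PMD point and no HoloSIM participant did, with all else equal, the mean difference would be 1 point. That is inside the 3-point limit.

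**Step 4. Look for another measure in Phase II.**
- The anaphylaxis knowledge test is a secondary outcome for declarative knowledge.
- SET-M has self-rated items on communicating with the patient and reporting to the team. It is a learning satisfaction tool completed after the practice session and is not part of the primary outcome.
- The usability questionnaires are completed only where HoloSIM is used.

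None of these is an observed rating of non-technical performance, so the Figure 6 checklist is the only observed performance measure.

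No revised sample size follows from any of this, because the mismatch is between construct and instrument.

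**The case against.** The strongest reply is that the protocol leaves non-technical skill undefined, and that a definition limited to teamwork and leadership is brought in from outside. The construct the document keeps naming is decision making: in the research questions section, in Platform design, in Randomization and Study Groups, and in the title of Figure 6. On that reading the checklist scores clinical steps together with the decisions behind them. The protocol also never promises separate results; it sets one outcome, one limit and one comparison of means.

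Much of this stands, and it rules out several stronger readings that a reader might infer.

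- *The non-technical question cannot be answered at all.* This is not supported. Decision making can reasonably be counted as a non-technical skill, and the checklist may reflect it.
- *The score is blind to non-technical differences.* Counting item labels does not measure sensitivity. More than half the points credit gathering information about the patient, and poor prioritisation or coordination that led to missed steps would lower the total.
- *HoloSIM may well be worse for team behaviour, and the trial would miss it.* Platform design mentions a holographic team confederate, but nothing in the document indicates a deficit. Study follow-up does not say whether a team is present in the assessment scenario.
- *The checklist is the only instrument.* Phase II also has a knowledge test and questionnaires; the checklist is the only observed measure of performance.

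What the reply does not remove is the wording. The claim names two constructs, the protocol does not say which items belong to which, and all items enter one total. Even with decision making as the non-technical part, a total within the limit says nothing distinct about it.

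**Conclusion.** The mismatch is real and lies in the wording of the claim. Of 45 points, none rates leadership, task allocation or teamwork, at most 1 (2.2%) touches communication between clinicians, and no subscale isolates decision making. A result within the 3-point limit supports a statement about completing core anaphylaxis assessment and management steps. It does not support a separate statement about non-technical skills.

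This rests on Figure 6 being the whole scoring tool for the follow-up scenario, as Study follow-up indicates, and on no other observed rating being planned.

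A reader might go further and treat the primary comparison as invalid. The document does not support that: the comparison remains interpretable as a difference on a 0–45 checklist, with its limit set on the same scale. The claim should be corrected because it is wrong as written, but the defect does not threaten the conduct of the trial.

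**What to change.** Restate research question 2, the hypothesis and the Phase II primary outcome as *performance of core anaphylaxis assessment and management (decision-making) steps, Figure 6 checklist, 0–45*, and remove nontechnical from the non-inferiority claim. Make the same change where the wording recurs in Background and Rationale and in Overall Experimental Strategy and Workflow.

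The cost is a text amendment and a narrower claim. The limit of 3 points, the calculated sample size of 28, the recruitment target of 40, the scoring and the procedures do not change.

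Adding a behavioural rating of the videos is not needed for this correction. It would add assessor time, and it may not be scoreable, since the protocol does not say that the assessment scenario includes a team.
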